
Statistical Methodology:
	
Part A: Phase 1
 
The Phase 1 dose-escalation portion of the study will utilize the Bayesian optimal interval design (BOIN). Once the Dose Escalation is completed, the MTD will be selected based on isotonic regression. Specifically, the dose for which the isotonic estimate of the toxicity rate is closest to the target toxicity rate is the MTD that will be selected. If there are ties, the higher dose level will be selected when the isotonic estimate is lower than the target toxicity rate and the lower dose level will be selected when the isotonic estimate is greater than or equal to the target toxicity rate.
 
Approximately 16 patients will also be evaluated in a fed/faasted randomized crossover, single-dose lead-in phase to assess the effect of food on the PK of BDTX-189 400 mg.
 
Part B: Phase 2
 
Sample Size Considerations: The target objective response rate (ORR) is defined to be 30% or greater for Cohorts 1 and 2, and 20% or greater for Cohorts 3, 4, and 5. The null ORR (i.e., an ORR of no interest) is determined to be 17.5% or less for Cohorts 1 and 2, 5% or less for each subgroup in both Cohorts 3 and 4, and 10% for Cohort 5. Sample sizes were estimated based on a Simon 2-stage optimal design with some modifications. That is, a 3-stage design will be created for Cohorts 1 and 2, while a 2-stage design will be created for each of five subgroups in Cohort 3, each of three subgroups in Cohort 4, and Cohort 5. The sample size for a cohort/subgroup was estimated using a 1-sided test at the nominal 5% level of significance, with a nominal power of 80% to detect the target ORR. A total of up to 491 patients will be enrolled to Part B: approximately 85 to each of Cohort 1 and Cohort 2, approximately 29 in each of the five subgroups in Cohort 3 and each of the three subgroups in Cohort 4, and approximately 89 to Cohort 5.
 
Futility Analysis: Decision rules are created separately for each cohort (subgroup) to support the primary objectives of that cohort (subgroup). Assessment of the early termination futility analysis will be based upon the response assessments conducted up to and including 6 weeks after first dose of study drug (Section 7.3.3) and will not require confirmation.
 
Final Analysis: Disposition summary will be based on the intent to treat population that will include all patients that signed informed consent. Safety and efficacy analyses will be based on the full analysis set that includes all patients enrolled and who received at least 1 dose of study drug treatment. The final analysis of ORR will be based on the best overall response of CR or PR observed during the study, as per RECIST v1.1. All categorical parameters will be presented by number and percent of patients for each category, along with 2-sided 95% confidence intervals (CIs). Time-to-event endpoints will be evaluated using Kaplan-Meier survival analysis. Kaplan-Meier curves will be generated, and the median time-to-event and

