9.2. Estimands

The primary estimand for Part A is the rate at which DLTs occur after treatment with BDTX-189 when administered either QD or BID. It is further described by the following attributes:

- Population: Patients with advanced solid malignancies as reflected by the inclusion/exclusion criteria outlined in Sections 3.1 and 3.2.
- Variable: DLTs, as defined in Section 4.3.2, occurring during the first 21 days of treatment (i.e., Cycle 1).
- Population-level summary: DLT rate, which is defined as the proportion of patients who experience a DLT during Cycle 1. Separate summaries will be estimated for each evaluated dose level of BDTX-189.
- Intercurrent events: Estimation will be based on the hypothetical situation that all patients either receive at least 75% of their planned doses of BDTX-189 during their first 21 days of treatment or experience a DLT during their first 21 days of treatment (i.e. are considered DLT-evaluable). Patients who are DLT-evaluable will be included in the calculation of the DLT rate. Additional patients will be enrolled, if necessary, to ensure an adequate number of DLT-evaluable patients.

The primary estimand for Part B is the effect of BDTX-189, when administered at the RP2D, on objective response rate as assessed by BICR and per RECIST v1.1. It is described by the following attributes:

- Population: Patients with solid tumors containing mutations falling into one of the MTC-A through MTC-G groupings as reflected by the inclusion/exclusion criteria outlined in Sections 3.1 and 3.2.
- Variable: Objective responses defined as CR or PR as assessed by BICR and per RECIST v1.1, which occur from the date of first dose of study treatment until the date of the first documentation of PD, death or start of new anti-cancer therapy. Objective responses must be confirmed by repeat assessments performed at least 4 weeks later.

- Population-level summary: Objective response rate, defined as the proportion of patients in the analysis population with an objective response. Separate summaries will be estimated for various combinations of MTC groupings and tumor types.
- Intercurrent events: Estimation will be based on a “while on treatment” strategy. Patients who do not have a post-baseline tumor assessment or patients who receive subsequent anti-cancer therapies, have PD, die, or otherwise stop tumor assessments prior to experiencing a CR or PR will be considered non-responders.

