9.3.2. Phase 2 (Part B)

For Cohorts 1, 2, and 5, the sample size was determined for each cohort independently. For Cohorts 3 and 4, the sample size was determined for each subgroup within a cohort independently.

The rationale for the different null hypotheses and target ORR values for each cohort/subgroup is discussed in Section 4.2.

Sample sizes for Cohorts 1-5 were estimated using nQuery version 8.6. The following sections provide the details of sample size considerations for each cohort and a summary of sample size for each cohort for various scenarios.

9.3.2.1. Sample Size Considerations for Cohorts 1 and 2

The sample size in each cohort will be based on a Simon 2-stage optimal design ([Simon 1989](#)), with the modification of adding an additional earlier assessment of futility. Therefore, Cohorts 1 and 2 will be evaluated in 3 stages.

Each cohort is designed to provide approximately 80% power to detect a true target ORR of 30%, while rejecting a null ORR of 17.5% at a nominal 1-sided alpha level of 0.05. For each cohort, 15 patients will initially be enrolled. If no patient has an objective response at the end of Stage 1, enrollment to the cohort will stop, otherwise an additional 16 patients will be enrolled. If 6 or fewer of the 31 total patients have objective responses at the end of Stage 2, enrollment to

the cohort will stop, otherwise an additional 54 patients will be enrolled. The null hypothesis will be rejected if at least 21 of the 85 total patients have objective responses.

A small number of first-line NSCLC patients may be enrolled to Cohort 1, in which case, these patients will be analyzed separately and will not count towards the numbers of patients described above.

[Table 12](#) provides the operating characteristics for Cohorts 1 and 2.

Table 12 Operating Characteristics for Cohorts 1 and 2

	Cumulative Probability of Stopping for Futility (Number of Responders/Total N) ¹			
	Stage 1 (0/15)	Stage 2 (≤ 6/31)	Stage 3 (≤ 20/85)	
True ORR = 17.5%	0.0558	0.7081	0.9541	Overall Type I Error: 0.0459
True ORR = 30%	0.0047	0.1355	0.1992	Overall Type II Error: 0.1992

¹ Based on exact binomial distribution.

9.3.2.2. Sample Size Consideration for Cohort 3

Cohort 3 will include 5 distinct mutational type subgroups (MTC-B, MTC-C, MTC-D, MTC-E and MTC-F) with each being evaluated independently.

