9.5.3. Efficacy Analysis

The Investigator-assessed objective response is a secondary endpoint for Part A. BICR-assessed objective response is a primary endpoint for Part B. Secondary objectives of Part B include evaluating the Investigator-assessed objective response, and evaluating both the Investigator and BICR-assessed duration of response (DOR), disease control rate (DCR), and PFS as evidence of the antitumor activity of BDTX-189. Evidence of antitumor activity for ORR, DOR, DCR, and PFS will be determined by RECIST v1.1. OS is also a secondary endpoint for Part B.

- Objective Response Rate (ORR), defined as the proportion of patients with a best overall response of CR or PR recorded from baseline until PD, start of subsequent anti-cancer therapy, or death due to any cause according to the RECIST Version 1.1 criteria (see [Appendix B](#)). The Part B primary endpoint will be based on the confirmed ORR (i.e., 2 CRs or PRs at least 4 weeks apart). Unconfirmed best overall response and response rates will also be summarized.
- Duration of Response (DOR), defined as the time between first documentation of a response (CR or PR) and first evidence of PD according to RECIST v1.1 or death due to any cause. In case a patient does not have progression or death, DOR is censored at the date of last adequate tumor assessment (defined as an assessment of CR, PR, or SD). Duration of response analysis will include only the responders.
- Disease Control Rate (DCR) is defined as the proportion of patients with a best overall response of CR, PR, or SD.
- Progression-Free Survival (PFS), defined as the time from the first day of study drug administration to PD as defined by the RECIST Version 1.1 criteria, or death. Patients who are alive and free from PD will be censored at the date of last adequate tumor assessment.
- Overall Survival (OS), defined as the time from the first day of study drug administration to death. Patients who are alive will be censored at the last date the patient was known to be alive.

For ORR and DCR, patients without an adequate post-baseline tumor assessment will be classified as NE and considered non-responders. ORR estimates and the associated 95% CIs (based on exact binomial distributions) in each cohort/subgroup will be calculated.

For PFS and OS, Kaplan-Meier curves will be generated, and the median time-to-event and the associated 2-sided 95% CIs will be provided.

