9.6.2. Planned Interim Analysis

To minimize exposing patients that may be unresponsive to BDTX-189 therapy in Part B, the plan is to apply the stopping rules described in Section 9.6. The interim analysis for each cohort will be conducted once the required number of patients have been enrolled and have either undergone at least 1 postbaseline tumor assessment or discontinued treatment for any reason prior to their first postbaseline tumor assessment.

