10.3.2. Data Monitoring Committee (Part B Only)

To provide independent oversight of safety and efficacy, a data monitoring committee (DMC) will be instituted. The DMC will meet regularly to ensure that patient safety is carefully monitored. The DMC will convene to review relevant data determine if each stage can proceed to the next based on the futility boundaries for each cohort as described in Section 9.3.2. The DMC will convene additional ad hoc meetings if necessary. Following each meeting, the DMC will recommend continuation, modification, or discontinuation of each cohort and/or subgroup. A separate DMC charter will describe the activities of this committee in more detail.

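### Futility looks count unconfirmed response up to Week 6, but Tables 12 to 15 assume interim and final response are the same variable, so the stated operating characteristics belong to a different rule

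*Combined protocol and SAP*

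**What the plan says.** **At the looks.** The Futility Analysis paragraph of the Synopsis says the assessment "will be based upon the response assessments conducted up to and including 6 weeks after first dose of study drug" and that confirmation is not needed. With scans every 6 weeks (Section 5.3.3), that window holds one scheduled scan. Section 9.6.2 times the look for when the required patients "have either undergone at least 1 postbaseline tumor assessment or discontinued treatment" before that scan. It sets no Week 6 cap and does not mention confirmation.

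**At the end.** Section 9.2 defines the Part B variable as BICR-assessed CR or PR from first dose until progression, death or new anti-cancer therapy, and adds: "Objective responses must be confirmed by repeat assessments performed at least 4 weeks later". Section 9.5.3 agrees: "The Part B primary endpoint will be based on the confirmed ORR (i.e., 2 CRs or PRs at least 4 weeks apart". The Final Analysis paragraph of the Synopsis does not mention confirmation.

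**Bounds and tables.** Section 9.3.2 uses the single term objective response for both the interim and the final counts. Tables 12 to 15 carry one true ORR through every stage by exact binomial. The DMC decides whether each stage proceeds "based on the futility boundaries for each cohort as described in Section 9.3.2".

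**Cross-references.** The Synopsis cites a Section 7.3.3, but Section 7 has no subsections. Section 9.6.2 says "the plan is to apply the stopping rules described in Section 9.6", whereas those rules are in Section 9.3.2. The protocol does not say whether BICR or Investigator reads are used at the looks.

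**The concern.** A patient can be classified differently at the look and at the end, in two ways. A response first seen after Week 6 is a failure at the look but can be a success at the final test. A Week 6 response that never confirms is a success at the look and a failure at the final test.

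The two errors pull in opposite directions. If late responses dominate, active cohorts are stopped too often and power falls. If unconfirmed early responses dominate, power holds or rises, but fewer inactive cohorts are stopped. That works against the purpose given in Sections 4.2 and 9.6.2, which is to limit the exposure of patients unlikely to respond. Either way, the DMC applies bounds whose published properties were computed for another rule.

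**Working it through.** **Inputs from Section 9.3.2**
- Cohorts 1 and 2: null 17.5%, target 30%; stop at 0/15 or at 6 or fewer of 31; reject at 21 or more of 85.
- Each Cohort 3 or 4 subgroup: null 5%, target 20%; stop at 0/10; reject at 4 or more of 29.
- Cohort 5: null 10%, target 20%; stop at 3 or fewer of 30; reject at 14 or more of 89.

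**Step 1: reproduce the tables.** One response probability is used at every stage, and paths at or below a futility bound are removed.

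| Design | Stop, null | Stop, target | Type I | Power |
|---|---|---|---|---|
| Cohorts 1, 2 | 0.0558, then 0.7081 | 0.0047, then 0.1355 | 0.0459 | 0.8008 |
| Cohort 3, 4 subgroup | 0.5987 | 0.1074 | 0.0468 | 0.8011 |
| Cohort 5 | 0.6474 | 0.1227 | 0.0478 | 0.8018 |

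These match Tables 12 to 15 (power = 1 − type II error). The sponsor's arithmetic is correct for a single variable.

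**Step 2: separate the two variables.** Let p be the true confirmed ORR. Two quantities are assumed because the protocol gives neither:
- f = share of eventual confirmed responders already in CR or PR by Week 6;
- g = share of all other patients with an unconfirmed Week 6 response.

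Each patient falls in one of four cells (interim, final), with probabilities:
- yes, yes: pf
- no, yes: p(1 − f)
- yes, no: (1 − p)g
- no, no: (1 − p)(1 − g)

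An exact recursion on the two counts applies the futility bounds to the interim count and the final bound to the confirmed count. Setting f = 1 and g = 0 returns Step 1.

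Stopping depends only on the interim rate r = pf + (1 − p)g, so a Cohort 3 or 4 subgroup can be checked by hand. Under the null with f = 0.9, g = 0.05:
- r = 0.05 × 0.9 + 0.95 × 0.05 = 0.0925
- P(stop) = (1 − 0.0925)^10 = 0.379, against 0.95^10 = 0.599 in Table 13
- expected patients = 10 + 19 × (1 − 0.379) = 21.8, against 10 + 19 × (1 − 0.599) = 17.6

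**Step 3: results for Cohorts 1 and 2**

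| f | g | Power | Stop at target | Stop under null | Type I |
|---|---|---|---|---|---|
| 1 | 0 (Table 12) | 80.1% | 13.6% | 70.8% | 4.6% |
| 0.9 | 0 | 72.3% | 23.0% | 79.4% | 3.8% |
| 0.8 | 0 | 60.9% | 36.0% | 86.7% | 2.8% |
| 0.9 | 0.05 | 80.3% | 12.3% | 57.9% | 4.8% |
| 0.8 | 0.10 | 80.5% | 11.2% | 44.9% | 4.9% |
| 1 | 0.10 | 86.8% | 2.9% | 28.0% | 5.6% |

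**Step 4: all designs, f from 0.8 to 1.0 and g from 0 to 0.10**

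| | Cohorts 1, 2 | Cohort 3, 4 subgroup | Cohort 5 |
|---|---|---|---|
| Power | 60.9–86.8% | 74.7–83.9% | 68.0–86.6% |
| Stop under null (stated) | 28.0–86.7% (70.8%) | 20.9–66.5% (59.9%) | 15.2–78.4% (64.7%) |
| Type I | 2.8–5.6% | 4.2–5.2% | 3.6–5.7% |
| Type I if futility never stops | 5.9% | 5.5% | 5.9% |
| Expected N under null, as designed | 45.9 | 17.6 | 50.8 |
| Same, f = 0.9, g = 0.05 | 53.2 | 21.8 | 64.9 |
| Same, f = 1, g = 0.10 | 69.7 | 25.0 | 80.1 |

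The type I ceilings are the single-stage tails P(X ≥ 21 of 85 at 0.175) = 0.0587, P(X ≥ 4 of 29 at 0.05) = 0.0548 and P(X ≥ 14 of 89 at 0.10) = 0.0587. Expected N ignores patients accrued while a look is pending.

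**Step 5: the only related data in the protocol.** Section 1.1.2 reports, for another drug in breast cancer, 8/25 responses at week 8 and 6/25 overall. If all six overall responders had responded by week 8, then f = 1 and g = 2/19 = 0.105. A Cohort 3 subgroup would then stop under the null 19.7% of the time instead of 59.9%, with power 84.0% and type I error 5.2%. This points to weaker futility rather than lost power. It is one small sample at a different week, and it cannot separate f from g.

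**The case against.** The strongest reply is that the Week 6 cap and the waiver of confirmation appear only in the Synopsis. Section 10.3.2 sends the DMC to Section 9.3.2, which speaks only of objective responses, and Section 9.2 defines those as confirmed BICR responses. Early enrollees will also have later scans by the time of a look, and counting those would shrink the mismatch. This is fair, and it shows that the rule is inconsistent as well as mis-modelled. It does not remove the mismatch: Section 9.6.2 lets the look proceed when patients have had only one post-baseline scan, and a response first seen on that scan cannot yet be confirmed.

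Other points on that side have some weight:
- The stopping columns are right if true ORR is read as the rate at the look. For example, f = 0.8, g = 0.05 and p = 0.20 give r = 0.16 + 0.04 = 0.20. The tables, however, use the same figure as the confirmed rate at the final test.
- f and g are assumed and the grid is a choice. Mild departures change power little: f = 0.95, g = 0.02 gives 79.5%, 80.3% and 80.9% across the three designs. Extending f down to 0.5 takes Cohort 1 and 2 power as low as 17%.
- Section 7.3.3 is probably the former number of Section 5.3.3 (Response Assessments), since the Amendment 3 summary reports renumbering.
- Appendix B puts the first scan at 42 ± 3 days, so whether a scan on the late side of the window counts is a wording matter.
- The DMC charter and imaging charter are separate documents and may name the interim assessor.
- The DMC recommends rather than stops automatically, so modelling the looks as binding is a simplification.

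**Conclusion.** The concern holds. The power, type I errors and stopping probabilities in Tables 12 to 15 are exact for a rule in which interim and final response coincide, and the written futility rule is not that rule. An early unconfirmed futility endpoint is a legitimate choice; the defect is that its properties are not stated.

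The direction is unknown because the protocol gives neither f nor g. Power can stay near 80% while futility protection weakens: at f = 0.9, g = 0.05, Cohort 1 and 2 power is 80.3% but stopping under the null falls from 70.8% to 57.9%. With late responders only (f = 0.8, g = 0), power falls to 60.9%. False-positive risk is a minor issue, since the final bounds cap type I error at 5.9%, 5.5% and 5.9%. The figures assume independent patients, the same f and g under null and target, looks that are always obeyed, and the Week 6 cap applied to every patient. This should be fixed before the first Part B look.

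**What to change.** 1. Define the interim response once, in the same terms in the Synopsis, Section 9.6.2 and the DMC charter: the window, whether confirmation is needed, whether later scans of early enrollees count, and the named assessor. State that the first scheduled scan counts with its ±3-day window.
2. Keep the early unconfirmed endpoint if it is wanted, but recompute Tables 12 to 15 with interim and final status as two variables over a stated range of f and g. Report power, type I error, stopping probabilities and expected sample size, and revisit the interim bounds if the results are unacceptable.
3. Correct the cross-references: replace Section 7.3.3 in the Synopsis, and point Section 9.6.2 to Section 9.3.2. Add the confirmation requirement to the Final Analysis paragraph of the Synopsis.

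The cost is a recalculation and some wording. Patient numbers and timing do not change if the early endpoint and current bounds are kept. Naming BICR as interim assessor means central reads must be ready at each look; Section 5.3.3 currently describes central reading as a future step that depends on Part A results. Moving the cut to Week 12 is possible, but it delays each look, exposes more patients if accrual continues, and would not by itself make the tables exact.
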